In this clinical trial, 70 - 140 patients undergoing surgery treatment for thyroid cancer will be enrolled into one of three treatment arms. Patients receiving total thyroidectomy for papillary thyroid cancer (PTC) with no pre-operative evidence of distant or cervical lymph node metastasis will be randomized into one of two arms: prophylactic central neck dissection or no central neck dissection. Patients who are not eligible for randomization will be enrolled into a third standard of care arm. We will then compare the three cohorts: (1) To determine the rate of transient and persistent hypocalcemia; (2) To determine the rate of voice and swallowing problems; (3) To determine the degree to which HR-QOL is compromised; (4) To determine clinical recurrence rates; (5) To determine the degree to which Natural Language Processing (NLP) tools can extract and document quality of life measures from patient interview narratives; (6) To determine the extent of correlation among quality of life measures obtained from patient interview narratives and those from traditionally administered quality of life surveys.

Figure 1: Trial overview diagram

Schedule of activities

	Visit 1	Visit 2	Visit 3	Visit 4	Visit 5		Visit 6	Visit 7	
	Screening	Day of Operation	Post-Op	Day 12	Week 6	Cancer Screen	Month 6	1 Year	Follow-up
Window	6 weeks-24 hours before operation		0-2 days	± 8 days	4-20 weeks	+2-7 days after Week 6	±6 weeks ¹	10 – 18 months	+10-19 months (+1-6 weeks post 1 year)
Informed Consent Obtained	X								
Venipuncture	SOC		SOC	SOC	SOC	SOC ^{2, 3, 4}	CI	SOC	
Calcium ³	SOC ³		SOC ^{3, 5}	SOC ^{3, 5}			X ^{5, 17}	CI ^{5, 17, 18}	
Parathyroid Hormone (PTH) ³	SOC ³		SOC ^{3, 5}	SOC ^{3, 5}			X ^{5, 17}	CI ^{5, 17, 18}	
Vitamin D ¹⁷	CI ^{6, 17}								
Neck Ultrasound	SOC ⁷						SOC	SOC	
Chest X-ray ⁸	SOC ⁸								
Comprehensive Voice Evaluation: Phonation Threshold Pressure, Dysphonia Symptom Index, CAPE-V, GRBAS, Stroboscopy, Glottal Function Index, VHI	CI ⁹			CI ⁹	CI ¹⁰		CI ¹⁰	CI ¹⁰	
Swallow Evaluation: standardized videofluoroscopic swallow study ¹⁵	X ¹¹			CI ¹¹	CI ¹¹		CI ¹¹	CI ¹¹	
Quality of Life Surveys, including: (1) the Short Form 12 (SF-12, Medical Outcomes Trust); (2) The European Organization for Research and Treatment of Cancer QOL instrument (EORTC QLQ C30); (3) The Voice Handicap Index (VHI) for assessing voice-related QOL (part of voice evaluation); (4) the EAT-10 Swallow Instrument; (5) Thyroid Cancer QOL (Thy-Ca QOL)	X			X	X		X	X	

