2.2. Secondary outcomes and endpoints

To determine the rate of voice and swallowing problems, patients will receive videofluoroscopic swallowing studies and voice evaluations pre-operatively and post-operatively (at Day 12, Week 6, Month 6, and 1 Year visits) to examine how voice and swallow function are affected by inclusion of a CND. Voice and/or swallow evaluations may be eliminated once necessary endpoints have been satisfied or the evaluation is no longer informative.¹

- Phonation Threshold Pressure (cm H₂O)
- Dysphonia Severity Index (DSI; +5 to -5)
- GRBAS (grade roughness breathiness asthenia strain)
- CAPE-V (0-100 on visual analog scale for voice quality parameters)
- Stroboscopy assessment (ratings 1 [most severe] to 4 [normal]) for vocal fold vibratory and movement parameters
- Glottal Function Index score
- Penetration-Aspiration Scale (0-8 score) from videofluoroscopic swallow study¹

To determine the degree to which quality of life (QOL) is compromised, qualitative analyses of patient interview data and validated surveys of general health quality, as well as QOL surveys specific to cancer, thyroid disease, voice and swallowing will be used to assess the impact of complications on patient's lives.

- SF-12 MCS and PCS scores
- EORTC QLQ C30 scale scores
- ThyCA-QOL score
- EAT-10 dysphagia inventory score
- VHI score (collected by UW ENT department during the participant's voice evaluation, and by study personnel if no voice evaluation is needed)
- Themes, codes from interview transcripts (using qualitative research methods)

¹ With the elimination of swallow studies for patients enrolled after 12/01/2016 collection of data for this endpoint ceased.

To determine whether accurate quality of life measures can be extracted from patient interview narratives, patient interview data will be converted into usable datasets using natural language processing techniques and is then compared to QoL surveys specific to cancer and thyroid disease.

- Interview transcripts
- SF-12 MCS and PCS scores
- EORTC QLQ30 scale scores
- ThyCA-QoL score

To determine clinical recurrence rates, measures of thyroglobulin levels (a reliable surrogate marker for future recurrence), and clinical evidence of recurrent disease (using either I-131 imaging or neck ultrasound), will be made at Month 6 and 1 Year visits.

- Percent of patients with a 1 Year recombinant thyroid-stimulating hormone (rTSH) stimulated Thyroglobulin level <1 ng/ml

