At each time point (pre-operatively, post-operative, 6 weeks after surgery, 6 months after surgery, and 1 year after surgery), a semi-structured qualitative interview will be conducted by a trained interviewer who is not a member of the clinical staff. Interview guides were developed in consultation with clinical

staff and piloted prior to use; guides include both prompted and unprompted open-ended questions aimed at understanding patient experience with various components of thyroid cancer treatment and subsequent care. All interviews will be transcribed verbatim and any identifiers will be removed from transcripts prior to coding. Data will be coded using a catalogue of focused codes developed through analysis of emergent themes in a representative subset of interview transcripts. Qualitative Health Research Consultants (QHRC), a NIH approved subcontract consisting of [name], [name], and their employees, will assist with data collection and analysis associated with qualitative aims.

Patients will also be contacted after their one year study time point to complete an electronic questionnaire about their study participation for the purposes of quality improvement, to better understand patient's perceptions of their participation in a clinical trial, and to give patients the opportunity to receive updates on study-related research in the future.

Additionally, we would like to use the coded transcripts from the interviews to customize Natural Language Processing (NLP) tools; Doing this will provide a usable training dataset from coded quality of life (QOL) surveys that the patients completed on the day of each interview. We will train NLP algorithms to turn patient narratives (transcribed interview text) into quality of life measures. That is, we aim to predict how a person would fill out a given quality of life survey tool based on their interview text. The following describes the development process:

1. The interview recordings will be transcribed by trained transcriptionists employed through the Wisconsin Surgical Outcomes Research Program (WiSOR) or an outside contractor with a business associate agreement that has been approved by UW Legal Services/Privacy Officer for HIPAA compliance. Transcriptionists have been instructed to remove identifying information from the transcripts. The audio recordings and transcripts will be shared through a secure server that only the transcriptionists and study team members have access to.

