2. The completed interview transcripts will be stored on the secure network within the Wisconsin Surgical Outcomes Research Program (WiSOR). The main levels of security for this data application server housed at the SMPH Computer Center include: being securely located behind the UW-Madison campus firewall; having data directory access controls; having physical server security; and having virtual server security. The participants' names and identifying information will be stored separately from the interview transcripts. The only link between the transcripts and the identifying information will be a subject identification number contained in both data files.
3. The transcripts will be reviewed and patient narratives pertinent to quality of life will be extracted.
4. Natural language processing (NLP) tools will be used to parse the patient narratives and extract quality of life measures. A variety of parsing and machine learning strategies will be employed to maximize accuracy. Collaborators in the Department of Journalism and Mass Communications will assist with the development of these tools. All resulting data files will be stored on secure and encrypted servers.
5. The accuracy of the NLP tools will be evaluated by comparing computer generated quality of life responses to the actual patient responses and collected QOL surveys
6. The NLP tools will be customized as needed to make extraction as accurate as possible. Again, a variety of software packages and/or machine learning programming will be employed.

4. Study population

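### The NLP steps specify no held-out patients or cross-validation and re-tune the tools after scoring them, so accuracy reported for the NLP aim is likely to be inflated

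*Combined protocol and SAP*

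**What the plan says.** The Summary lists as its fifth aim: "To determine the degree to which Natural Language Processing (NLP) tools can extract and document quality of life measures from patient interview narratives". Section 2.2 makes this a secondary outcome, "To determine whether accurate quality of life measures can be extracted from patient interview narratives", to be answered by comparing NLP output with the quality-of-life surveys.

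Section 3 describes how the tools are built.

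- **Data.** The coded trial interviews are paired with surveys completed on the same day: "Doing this will provide a usable training dataset from coded quality of life (QOL) surveys that the patients completed". No other corpus is named.
- **Training.** "We will train NLP algorithms to turn patient narratives (transcribed interview text) into quality of life measures".
- **Step 4.** "A variety of parsing and machine learning strategies will be employed to maximize accuracy".
- **Step 5.** "The accuracy of the NLP tools will be evaluated by comparing computer generated quality of life responses to the actual patient responses".
- **Step 6, the last.** "The NLP tools will be customized as needed to make extraction as accurate as possible".

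Interviews take place at five time points per patient. Section 8.2 (Analysis of endpoints) covers the primary aims and says nothing about validating the NLP tools.

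**The concern.** For this aim the accuracy figure is the result. Its credibility depends on which patients supplied it and whether the tools were still being adjusted to them.

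The stated order is to try several strategies, score them, then adjust to raise the score. With one corpus and no reserved patients, the data that shape the tools can also be the data that grade them. Repeated interviews add a second route for optimism: a tool can learn how a particular patient talks and where that patient usually scores, and then meet the same patient again in a test set drawn by interview.

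What is at stake is the use of the tools. Section 9.3 suggests that they could reduce the need for structured surveys, and an optimistic figure would support that wrongly.

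**Working it through.** The plan gives no NLP accuracy figure, metric or sample size, so there is nothing to reproduce. The check has two parts.

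**1. What steps 4 to 6 yield under each reading of step 5**

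- Step 5 uses the training interviews: the figure is same-data accuracy and is optimistic.
- Step 5 uses held-out interviews and is repeated after step 6: the held-out set has guided the customising, so it has become tuning data.
- Step 5 uses held-out interviews and is not repeated: the figure describes tools that step 6 then replaces.

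Under none of the three do the steps, as listed, give an untouched estimate for the final tools.

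**2. Illustration of size**

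From the documents: 70 to 140 randomised patients (section 8.1) and five interviews each (section 3), so at most 70 × 5 = 350 to 140 × 5 = 700 interviews from randomised patients.

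Assumed, because the documents give none of it: 20 to 200 text features; within-patient correlation 0.5 for features (ρx) and 0.6 for the residual part of the survey score (ρy); ridge regression with penalty 0.5 × number of features; 30 runs per setting.

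Model for patient i, interview j:

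- features: x = √ρx · aᵢ + √(1−ρx) · dᵢⱼ
- score: y = √R² · (x·w) + √(1−R²) · [√ρy · uᵢ + √(1−ρy) · eᵢⱼ], with w a unit vector

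Mean correlation between predicted and actual score, from 20 to 200 features:

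| Patients | True R² | Same data | 5-fold split by interview | 5-fold split by patient |
|---|---|---|---|---|
| 70 | 0 | 0.34 to 0.83 | 0.16 to 0.44 | −0.06 to 0.01 |
| 140 | 0 | 0.25 to 0.68 | 0.11 to 0.35 | −0.03 to −0.01 |
| 70 | 0.3 | 0.62 to 0.87 | 0.54 to 0.58 | 0.45 falling to 0.22 |
| 140 | 0.3 | 0.58 to 0.79 | 0.54 to 0.58 | 0.49 falling to 0.33 |

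With R² = 0.3 the best attainable correlation is √0.3 = 0.55, and every same-data value exceeds it. The gap between same-data and patient-level results grows with more features and fewer patients. These runs use one fixed model, so they leave out any further optimism from choosing among strategies or customising by hand.

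**Sensitivity of the interview-level leak** (no true signal, 20 to 100 features):

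- ρx = ρy = 0.6, 70 patients: 0.19 to 0.40
- ρx = 0.2, ρy = 0.6, 70 patients: 0.09 to 0.17
- ρx = 0, ρy = 0.6, 70 patients: about 0
- ρx = ρy = 0.3, 140 patients: 0.04 to 0.10

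The leak therefore depends on how strongly text features correlate within patients. Same-data optimism remains in all four settings.

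**The case against.** A reader might infer that the plan scores the tools on their own training interviews and that inflation is certain. The documents do not support that. Step 5 does not name its evaluation set, and comparing generated with actual responses describes a held-out comparison equally well. Section 3 also presents the steps as a development process, in which evaluating and then refining is normal, and never says that the step 5 figure is the one to be reported. This stands, and it is why the conclusion is conditional. It does not remove the problem: no later evaluation is described, and a held-out set used to guide step 6 is no longer held out.

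A reader might also extend the point to the sixth aim in the Summary. That aim concerns narrative-based measures and surveys and does not name NLP; narratives are also coded by qualitative methods. The point attaches to the fifth aim and to the NLP-survey comparison in section 2.2.

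The simulated sizes can fairly be called chosen inputs. Feature count, model, correlations and the no-signal case are all assumptions. Standard-of-care patients follow the same assessment schedule (section 1.2) and could enlarge the corpus, which would reduce the optimism. The direction survives this; the size does not transfer to the trial.

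**Conclusion.** The concern holds in conditional form. The plan specifies no held-out patients, no cross-validation and no evaluation after the final customising step. Carried out as written on the one corpus it names, the accuracy reported for the NLP aim is likely to be inflated, and a split by interview could still leak information.

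The size cannot be derived from the documents. The simulated gaps rest wholly on assumed feature counts, within-patient correlations and a ridge model, and show only that the inflation could be large enough to make uninformative text look useful.

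This is a secondary aim. Randomisation, the comparison of arms and the primary endpoint are untouched. It is a cheap improvement.

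**What to change.** Before any tuning, state the validation scheme and split by patient, keeping all interviews from one patient on the same side.

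- Where tuning is fully automated, use nested cross-validation with folds formed by patient.
- Where step 6 involves manual customising, which cannot readily be repeated inside folds, set patients aside at the start, lock the tools after step 6, and evaluate once on the untouched patients.
- Name the accuracy metric. Report accuracy and the NLP-survey correlations only from held-out patients, with an interval that allows for clustering by patient.

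**Cost.** Analysis work and a short addition to the plan, with no change to visits or data collection. A single hold-out leaves fewer transcripts for training and gives an imprecise estimate: 20% to 25% of 70 is 0.20 × 70 = 14 to 0.25 × 70 = 17.5, so about 14 to 18 patients. If the true correlation were 0.4 and both within-patient correlations 0.6 (assumed), the held-out correlation would have a 95% range of about 0.05 to 0.67 with 14 patients and 0.11 to 0.63 with 18. That width should be reported with the result.

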4.1. Inclusion criteria

Each patient must meet all of the following inclusion criteria to be enrolled in the study.

1. Pre-operative diagnosis or suspicion of papillary thyroid cancer, usually by FNA
2. No pre-operative evidence of cervical lymph node metastases on neck ultrasound
(Randomization arms ONLY)
3. No evidence of distant metastases
4. Age 21-73 years
5. Ability to read and write in English

4.2. Exclusion criteria

Patients meeting any of the following exclusion criteria are not to be enrolled in the study.

1. Largest papillary thyroid carcinoma <1 cm in size on ultrasound
2. Previous thyroid surgery
3. Concurrent active malignancy of another type
4. Age <21 or >73 years
5. Inability to give informed consent or lacks decision making capacity
6. T4 tumor
7. Pre-existing vocal cord paralysis
8. Chronic neurologic condition which affects voice or swallow (for instance, multiple sclerosis or Parkinson disease)
9. Baseline laryngeal pathology that would warrant intervention that could affect voice or swallow function
10. Becomes pregnant before surgery or at any time while on study

4.3. Intra-operation exclusion criteria (Randomization arms ONLY)

1. Evidence of nodal involvement identified in the OR
2. Failure to confirm diagnosis of cancer in participant

4.4. Protected populations

We will not be including any vulnerable populations, such as children, prisoners, those without decision making capacity or women known to be pregnant in this study.

5. Trial interventions

The intervention portion of this study is the assignment to Treatment Arm 1 (no CND) or Treatment Arm 2 (CND). SOC arm patients will not undergo any specific treatment intervention.

5.1. Treatment Arm 1 (No CND)

Arm 1: total thyroidectomy alone.

5.2. Treatment Arm 2 (CND)

Arm 2: total thyroidectomy with ipsilateral prophylactic CND

5.3. Treatment Arm 3 (SOC)

Arm 3: no specific trial intervention, treated as per patient and physician preference

5.4. Allocation to intervention

Patient allocation will be randomized by using a permuted block randomization stratified by age (\geq or $<$ age 45) as the staging of thyroid cancer is different based on patient age, and tumor size (T1-T2 vs. T3) as the benefit of prophylactic central neck dissection may be greater in patients with T3 tumors. We have no predefined recruitment goal for participants \geq or $<$ age 45. For tumor size we would like to recruit 25% of patients with T3 tumors (size $>$ 4 cm or minimal extrathyroidal extension); this is estimated to be 25% of our eligible population, so we believe that this goal is achievable. Randomization will occur on the day of surgery in the operating room after confirming no suspicious adenopathy and will only be known by the operating surgeon. Participants will be blinded to their treatment allocation until their 2-week follow up appointment at which time their pathology report will be reviewed and they will be told of their treatment allocation.

6. Participant recruitment and consent

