Eligible patients will have a thyroid nodule >1 cm in size that is consistent with or suspicious for PTC on a pre-operative biopsy. All biopsies will be reviewed by pathology to confirm eligibility. Patients with T4 (tumor of any size that extends beyond the thyroid) tumors, history of degenerative neurological diseases, pre-operative vocal cord paralysis or other vocal cord pathology will be excluded. All patients will undergo a comprehensive neck ultrasound to evaluate for lymphadenopathy by an experienced thyroid radiologist. A comprehensive evaluation of lymph nodes in levels 1-6 will be performed. If the patient is proven to have lymph node involvement they will be ineligible for the randomization arms.

Patients without evidence of nodal involvement on pre-operative imaging will be eligible for the randomization arms of the trial and consented pre-operatively. Per standard of care at our institution and the recommendations of the ATA, thyroid cancer patients are offered various surgical treatments depending on the nature of their disease. For example, for those whose cancer is limited to only one side of the thyroid, a partial lobectomy may be the appropriate treatment. For this reason, we will only approach patients who have elected to undergo total thyroidectomy for the randomization arms. Patients who are eligible for the trial but not for randomization (i.e. have evidence of lymph node disease or are choosing a thyroid lobectomy) will be approached for consent into the standard of care arm.

Pre-Operative Screening and Testing: Pre-operative laboratory testing will include calcium, PTH, and Vitamin D testing (Aim 1), a comprehensive voice and swallow¹ evaluation (Aim 2), and a complete quality of life evaluation using validated questionnaires and semi-structured interviews (Aim 3). Patients eligible for the randomization arms will then be randomly assigned - after intraoperative confirmation of no suspicious adenopathy or gross local invasion - to one of two treatments on the day of surgery; Arm 1: total thyroidectomy alone, or Arm 2: total thyroidectomy with ipsilateral prophylactic CND. Randomization will be stratified by both age and tumor size to allow appropriate comparisons between groups. Allocation schedule will not be known to study staff prior to consenting.

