8.2. Analysis of endpoints

For all primary aims, data will be analyzed using a mixed model two-way analysis of variance examining the effects of treatment group, time and factor interactions, such as radioactive iodine dose. Evaluation time periods (pre-surgery, Day 12, Week 6, Month 6, and 1 Year) will serve as between subjects factor and treatment group (prophylactic CND versus no CND) will serve as the between subjects factor. Experiment-wise error will be controlled with an appropriate adjustment to the alpha-level. Prior to each analysis, we will plot all data and carefully examine each analysis to ascertain that the assumptions of ANOVA are not violated. Data will be transformed as necessary to better conform to the assumptions. Nonparametric statistics will be used when assumptions for ANOVA are not achieved. Statistical support for the study design and analysis will be performed by [name] who will perform analyses with SAS statistical software (SAS Institute Inc., Cary, NC).

9. Risks and benefits of trial participation

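### Randomisation is stratified by age and tumour size, but section 8.2 commits to neither factor; if either predicts the outcome, a little precision and power is given away

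*Combined protocol and SAP*

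**What the plan says.** Section 5.4 sets out the allocation: "Patient allocation will be randomized by using a permuted block randomization stratified by age", with a cut at 45, and by tumour size in two classes, T1-T2 and T3. It gives a reason for each factor. For age: "as the staging of thyroid cancer is different based on patient age". For tumour size: "as the benefit of prophylactic central neck dissection may be greater in patients with T3 tumors". On the T3 share it says "this is estimated to be 25% of our eligible population". Section 3, under pre-operative screening and testing, gives the purpose: "Randomization will be stratified by both age and tumor size to allow appropriate comparisons between groups".

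Section 8.2 plans a "mixed model two-way analysis of variance examining the effects of treatment group, time and factor interactions, such as radioactive iodine dose". Its fallback is equally general: "Nonparametric statistics will be used when assumptions for ANOVA are not achieved". Neither age group nor tumour size appears there as a covariate, stratum or blocking term, and no stratified test is named. The sample size in section 8.1 is a plain two-proportion comparison (12% vs 36%, 58 per arm) without strata.

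**The concern.** Stratified permuted blocks keep the arms nearly balanced within each age-by-tumour-size cell. Any part of the outcome that differs between cells then largely cancels out of the arm difference. An analysis that ignores the cells still counts that between-cell variation as error. The reported standard error is then larger than the true one, so the test rejects less often than its nominal level and the interval is wider than it needs to be.

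A modest amount of precision is at stake, and only if the factors are prognostic. There is also a prespecification point. Because 8.2 leaves the covariates open, whether to adjust could be decided after the results are known.

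**Working it through.** **Inputs from the documents.** Rates 12% vs 36%, power 0.8, alpha 0.05, 58 per arm, and 70-140 to be randomised (section 8.1); T3 share 25% (section 5.4).

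**Assumptions not in the documents.** Block size 4, half the patients aged 45 or over, and every odds ratio and R² below. R² is the share of outcome variance explained by the strata.

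**Step 1: the plan's own figure.** With mean rate 0.24, two-sided, without continuity correction:

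n′ = [1.96·√(2·0.24·0.76) + 0.842·√(0.12·0.88 + 0.36·0.64)]² / 0.24² = (1.184 + 0.488)² / 0.0576 ≈ 48.5, that is 49 per arm.

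With the continuity correction, n = (n′/4)·[1 + √(1 + 4/(n′·0.24))]² ≈ 56.5, that is 57 per arm or 114 in total. This is within 2 of the stated 116, so the figure reproduces as an unstratified calculation.

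**Step 2: analytic range.** Let SE₀ = √(2·0.24·0.76/n), SE₁ = √((0.12·0.88 + 0.36·0.64)/n) and f = √(1 − R²).

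- Unadjusted interval width relative to adjusted: 1/f
- Unadjusted type I error: 2·[1 − Φ(1.96/f)]
- Unadjusted power: Φ[(0.24 − 1.96·SE₀)/(SE₁·f)]
- Adjusted power: Φ[(0.24 − 1.96·SE₀·f)/(SE₁·f)]

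Example at n = 58 and R² = 0.10: SE₀ = 0.0793, SE₁ = 0.0761, f = 0.949. Unadjusted power is Φ(1.171) = 0.879 and adjusted power is Φ(1.282) = 0.900.

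| R² | Unadjusted interval too wide by | Unadjusted type I error | Power, 58 per arm | Power, 35 per arm |
|---|---|---|---|---|
| 0 | 0% | 0.050 | 0.867 → 0.867 | 0.658 → 0.658 |
| 0.05 | 2.6% | 0.044 | 0.873 → 0.884 | 0.662 → 0.681 |
| 0.10 | 5.4% | 0.039 | 0.879 → 0.900 | 0.666 → 0.705 |
| 0.20 | 11.8% | 0.028 | 0.893 → 0.931 | 0.676 → 0.757 |

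**Step 3: simulation of the stratified design.** Pooled chi-square against Cochran-Mantel-Haenszel, 6,000 to 8,000 trials per scenario, with marginal rates held at 12% and 36% (24% in both arms under the null). Simulation error on a type I error is about 0.003.

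| Odds ratio T3 / age | Power, N=116 | Power, N=70 | Unadjusted type I error |
|---|---|---|---|
| 1 / 1 | no gain | no gain | about 0.05 |
| 2 / 1.5 | 0.882 → 0.884 | 0.678 → 0.683 | about 0.05 |
| 4 / 2 | 0.901 → 0.914 | 0.663 → 0.694 | 0.041-0.043 |
| 6 / 3 | 0.892 → 0.919 | 0.687 → 0.740 | 0.033-0.038 |

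The gains are under 1 point at 2/1.5, about 1.5-3 at 4/2 and about 3-5 at 6/3. At 1/1 the stratified test was lower by 0.3-0.4 points, within simulation error.

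**Step 4: sparse cells.** At N=70, with 25% T3 and an even age split, each T3-by-age cell holds 70 × 0.25 × 0.5 = 8.75 patients, or about 4.4 per arm. At a 12% rate, the arm without central neck dissection expects 4.4 × 0.12 ≈ 0.5 events in such a cell.

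**The case against.** A reader might infer that the trial stratifies because it expects both factors to drive the outcome, so that wide intervals and wasted power are certain. The documents do not support that. The stated reasons are staging for age and a possibly greater benefit of dissection for T3. Neither says that the factor predicts a Day 1 PTH below 10 pg/ml, the endpoint that sized the trial. Comparability of the arms, the purpose given in section 3, is served by the allocation itself.

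Four further points count against making much of this.

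- The larger odds ratios are strong assumptions. At 6 and 3, control-arm risk would run from about 3% (under 45, T1-T2) to 39% (45 or over, T3), with the strata explaining about 16% of outcome variance.
- The error is on the safe side. At N=116 the unadjusted test has power of about 0.88-0.90 in every scenario, above the planned 0.80.
- The chi-square comparator stands in for an analysis that 8.2 does not name. The section specifies a mixed-model analysis of variance, omits Day 1 from its time points, and gives no test for the binary endpoint.
- The words introducing radioactive iodine dose mark it as an example, so other factors are not excluded.

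All of this stands, and it limits the point to a conditional one. It does not remove it: leaving room for the strata is not a commitment to use them. Adjustment costs essentially nothing when the factors are not prognostic, and naming them closes a choice that is now open.

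**Conclusion.** The mismatch between design and analysis is real; its consequence is conditional and small. For Day 1 hypoparathyroidism the loss ranges from nothing to about 3-5 power points under the strongest odds ratios tried, with a test that is mildly conservative. These sizes rest on assumed odds ratios, block size and age split. They apply to a risk or mean difference; in a logistic model, adjustment need not shrink the standard error of the log odds ratio, although it generally gains power.

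Two stronger readings should be avoided. Ignoring the strata does not bias the comparison or inflate its type I error. Nor does adjustment rescue a trial of 70: even at odds ratios of 6 and 3 the stratified test reaches only about 0.74 against the planned 0.80. That shortfall comes from the smaller sample and is a separate matter. This point is a minor improvement at almost no cost.

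**What to change.** In section 8.2, prespecify for the two randomised arms, using age group and T-stratum as recorded at randomisation:

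- for Day 1 hypoparathyroidism, a Cochran-Mantel-Haenszel test with a Mantel-Haenszel weighted risk difference and its interval;
- for continuous outcomes, both factors as main fixed effects in every model;
- a rule for sparse strata, for example Mantel-Haenszel weights plus a stated order for pooling any stratum in which one arm is empty.

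A treatment-by-T-stratum interaction could be listed as exploratory, since a possible difference in benefit is the reason section 5.4 gives for that factor. The standard of care arm is not randomised and lies outside this change.

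The cost is analysis wording only. The strata have to be known before a patient can be allocated, so no new data are needed.
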